For infants in the attention control group, standard of care will be provided, including hands-on care by their nurses, diapering, swaddling, feeding, etc. After assessment and initial cares are completed, infants are tucked and nested with boundaries to support comfort, security, and flexion. The infants' hands are placed by their faces to encourage self-soothing, mouthing, and sucking. We will provide parents with two scent hearts to wear

and bring back to place near the infant's face. Parents perform routine care such as taking temperature, bathing, changing diapers, reading, feeding, and holding hands. Parents will have access to educational materials regarding preterm infant care such as Your Guide to Neonatal Intensive Care Unit and Breastfeeding in the NICU. Parents will receive an automatic daily text in the morning with a link to report their daily activities with infants when they visit the NICU. Parents in the attention control group will not have access to the M-MILK content.

vi. Study Assessments and Activities

1. Measures

Table 1. Concepts, Measures, and Operational Definitions

Concepts	Operational Definitions	Data Source & Time
Parent characteristics	Parent characteristics will include both mother and father as applicable. We will collect race/ethnicity, education, age at delivery, household income, number of children, number of children under 24 months, and social determinants of health (i.e., physical activity, financial resource strain, housing stability, transportation needs, food insecurity, stress, social connections, intimate partner violence, and alcohol use)	T0 EPIC & self-report
Maternal postpartum depressive symptoms	Maternal postpartum depressive symptoms are assessed by the Edinburgh Postnatal Depression Scale (EPDS). ³² The EPDS consists of 10 short statements. A mother checks off one of four possible answers that is closest to how she has felt during the past week. Responses are scored 0, 1, 2 and 3 based on the seriousness of the symptom. Items 3, 5 to 10 are reverse scored (i.e., 3, 2, 1, and 0). The total score is calculated by adding together the scores for each of the 10 items. Mothers scoring above 12 or 13 are likely to be suffering from depression and should seek medical attention. The pooled sensitivity and specificity of the EPDS were 0.81 and 0.87, respectively, with summary receiver operating characteristic curve of 0.90. ³³	T0, T3, T4 EPDS

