Postpartum Bonding Questionnaire	Parent-infant bonding will be evaluated by the Postpartum Bonding Questionnaire (PBQ). The PBQ comprises four subscales, i.e., general bonding disorders (12 items; 1, 2, 6, 7, 8, 9, 10, 12, 13, 15, 16, 17), severe mother-infant relationship disorders (7 items; 3, 4, 5, 11, 14, 21, 23), infant-focused anxiety (4 items; 19, 20, 22, 25), and risk of abuse (2 items; 18, 24). The total cumulative score, ranging from 0 to 125, is also used to screen for general bonding disorders (cut-off score ≥ 26), and severe bonding disturbances (cut-off score ≥ 40). The items are scored on a 6-point Likert scale (0-Always to 5-Never). Parents scoring ≥ 26 , (indicating risk of general bonding disorders) or ≥ 40 (indicating risk of severe bonding disturbances) should seek medical attention. Parents scoring "rarely", "sometimes", "quite often", "very often", or "always" for item 18 "I have done harmful things to my baby" or item 24 "I feel like hurting my baby" indicates risk of child abuse. In this case, it is our responsibility to report it to the state's child protective agency. If the infant is in immediate danger, the research staff will be instructed to inform the parents of their immediate concerns for the infant's safety, report the incident using a cellular phone, and call 911 until appropriate officials arrive. The PI will be informed of the family's condition and always be available by phone or in person for consultation and instruction. As part of the training of our research team, the team will review content related to reporting of child neglect and abuse.	T1, T3, T4 PBQ & Self-report
Pumping and breastfeeding	Mothers will report the following: pumping initiation date, pumping cessation date, pumping at discharge (yes/no), pumping at 2 months CA (yes/no), breastfeeding initiation date, breastfeeding cessation date, breastfeeding at discharge (yes/no), & breastfeeding at 2 months CA (yes/no).	Ongoing Self-report

Family daily NICU activities	Parents will report the following: (1) How many hours were you able to visit your baby today? (2) What activities did you do with your baby while you were visiting? The answer choices for question (2) for parents in the M-MILK group are: M-MILK, skin-to-skin, feeding, taking temperature, bathing, changing diaper, reading, holding hands.	Ongoing Self-report

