1. Risks Related to Study Procedure

During the study, if an infant becomes clinically unstable and/or develops new diagnosis, and no longer meet the inclusion criteria, we will remove the infant from the research protocol. The M-MILK intervention's safety has been demonstrated in infants as young as 22 weeks GA. According to the M-MILK protocol, nurses or parents will carefully observe infants' cues and responses during the M-MILK intervention and stop the administration if infants do not engage or exhibit any signs of distress. When collecting the buccal swab samples and administering NAPI, we will make every effort to be as gentle as possible and omit any item(s) that may be causing discomfort to infants. If parents report a score of 12 or above on the EPDS, we will make referrals to the NICU Social Worker. If parents report "yes, quite often" or "sometimes" to the question "the thought of harming myself has occurred to me" on the EPDS, we will refer the parent to the local Emergency Department immediately. For the PBQ, parents scoring ≥ 26 , (indicating risk of general bonding disorders) or ≥ 40 (indicating risk of severe bonding disturbances) should seek medical attention. For the PBQ, parents scoring "rarely", "sometimes", "quite often", "very often", or "always" for item 18 "I have done harmful things to my baby" or item 24 "I feel like hurting my baby" indicates risk of child abuse. In this case, it is our responsibility to report it to the state's child protective agency. If the infant is in immediate danger, the research staff will be instructed to inform the parents of their immediate concerns for the infant's safety, report the incident using a cellular phone, and call 911 until appropriate officials arrive. The PI will be informed of the family's condition and always be available by phone or in person for consultation and instruction. As part of the training of our research team, the team will review content related to reporting of child neglect and abuse.

2. Risks related to Data Confidentiality

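### The stated PBQ scoring names no reversed items, so a parent who never harms the baby gets the maximum risk-of-abuse score and 10 points toward the cut-off of 26

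*Combined protocol and SAP*

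**What the plan says.** The PBQ row of Table 1 (Section VII.a.vi.1, Measures) makes four statements that matter here.

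- Response scoring: "The items are scored on a 6-point Likert scale (0-Always to 5-Never". No item is excepted.
- Total: "The total cumulative score, ranging from 0 to 125". A high total is adverse: it "is also used to screen for general bonding disorders", with one cut-off given as "general bonding disorders (cut-off score ≥ 26" and a second, for severe disturbance, at 40.
- Subscales: four are listed, the last being "risk of abuse (2 items; 18, 24".
- Answer rule: any reply from *rarely* to *always* on "item 18 'I have done harmful things to my baby' or item 24 'I feel like hurting my baby' indicates risk of child abuse".

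Section VIII.b.ii.1 (Risks Related to Study Procedure) repeats the cut-offs and attaches the action: "indicating risk of severe bonding disturbances) should seek medical attention". It also repeats the answer rule for items 18 and 24, as does Section VIII.b.ii.3 (reporting of neglect and abuse). Neither section mentions reversal, and Section IX (Data Management and Analysis Plan) gives no scoring rules.

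The EPDS row of the same table does spell out its reversal: "Items 3, 5 to 10 are reverse scored".

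**The concern.** Scoring *always* as 0 and *never* as 5 fits a scale on which high is bad only if *always* is the healthy answer to every item. Items 18 and 24 are worded as harm, and the protocol's own answer rule makes *never* their only reassuring reply. On those two items the stated scoring therefore runs backwards.

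A programmer who follows the text would invert the abuse subscale and add wrong-way points to the total. The PBQ is collected at 34 weeks postmenstrual age, at discharge and at 2 months corrected age. Its total determines which parents are told to seek medical attention. Its spread is also part of the variability data that the third study aim is meant to supply for the planned larger trial.

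**Working it through.** **Inputs** (all from the PBQ row of Table 1): subscales of 12, 7, 4 and 2 items; item score 0 (*always*) to 5 (*never*); total range 0 to 125; cut-offs 26 and 40; abuse subscale = items 18 and 24.

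**Reproducing the plan's figure.** 12 + 7 + 4 + 2 = 25 items, and the listed numbers cover 1 to 25 once each. 25 × 5 = 125, the stated maximum. Items 18 and 24 are therefore part of the total.

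**Scoring items 18 and 24, same answer to both.** As written, the subscale is 2 × score. Reversed, it is 2 × (5 − score).

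| Answer to both | As written | Reversed |
|---|---|---|
| always | 0 | 10 |
| very often | 2 | 8 |
| quite often | 4 | 6 |
| sometimes | 6 | 4 |
| rarely | 8 | 2 |
| never | 10 | 0 |

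The ordering is fully inverted.

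**Effect on the screens.** A parent who answers *never* to both carries 10 points: 10/26 = 38% of the lower cut-off (26 − 10 = 16 left) and 10/40 = 25% of the upper (40 − 10 = 30 left). Let S be the sum of the other 23 items, assumed here to be scored in the right direction.

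- *Never* to both: total S + 10 as written, S if reversed. Parents with S from 16 to 25 wrongly screen positive at 26. Those with S from 30 to 39 wrongly screen positive at 40.
- *Always* to both: total S as written, S + 10 if reversed. The same ranges of S now give false negatives.

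**Effect on the summary statistics.** Let h be the correctly directed sum of the two items (0 to 10). The correct total is S + h; the total as written is S + 10 − h. The variances are Var(S) + Var(h) + 2Cov(S, h) and Var(S) + Var(h) − 2Cov(S, h), which differ by 4Cov(S, h). If h does not vary, the error is a constant shift and the SD is untouched. If parents with worse bonding also score worse on these items, the SD as written is too small.

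**The other items.** The documents show the wording of items 18 and 24 only. As an assumption, suppose k further items are also worded negatively and are answered *never*. The spurious total is then 10 + 5k. It reaches 26 at k = 4 (30 points) and 40 at k = 6 (40 points), with every other item at its healthiest score. The true k cannot be read from the documents.

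**The case against.** The strongest reply is that the row describes the response scale and is not a scoring key. It does not rule out reversal, and most other rows of Table 1 give no item-level key either. The plan says it uses validated instruments, and the cut-offs make sense only with one coherent direction, so the team may well score the PBQ correctly in practice. That is a fair account of intent. It does not rescue the text. The row states a direction for the items without exception, the neighbouring EPDS row shows that reversal is stated when it is meant, and the PBQ row cites no source. No title in the reference list names the PBQ, so the reader is pointed to no key that would correct the rule.

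Three further points stand and limit the consequences.

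- The child-protection trigger uses answer words, so it works the same under either scoring. No numeric cut-off is attached to the abuse subscale.
- The PBQ is not one of the feasibility criteria, and Section IX specifies no PBQ test.
- If every parent answers *never* to both items, the 10 points are a constant. They distort the subscale and both screens but leave the SD and any group difference alone.

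**Conclusion.** The concern holds. Read literally, the PBQ rule contradicts both the direction of its own cut-offs and its own answer rule for items 18 and 24. The demonstrable size is 10 points per parent answering *never* to both: the whole range of the abuse subscale, 38% of the lower cut-off and 25% of the upper.

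This rests on two readings. First, that no reversal is stated means that none would be applied by someone working from the protocol. Second, that a higher abuse-subscale score means more risk, which is inferred from the subscale's name and the direction of the total, since no subscale cut-off is given. Any error on the other 23 items would add to this but cannot be sized from the documents. The effect on the SD may be nil or may be material, depending on how much answers to these two items vary.

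**What to change.** In the PBQ row, replace the single scoring sentence with an item-level rule under which a higher score is worse throughout: positively worded items from 0 (*always*) to 5 (*never*), and negatively worded items, including 18 and 24, from 0 (*never*) to 5 (*always*). Take the full list of reversed item numbers from the instrument's published key, print it as the EPDS row does, and cite the key. Then check that whatever computes the score, in REDCap or SAS, follows it. Two test records suffice for items 18 and 24: *never* to both should return 0 on the abuse subscale, and *always* to both should return 10. Rescore any PBQ data already summarised.

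The total range stays 0 to 125. The scoring direction, the cut-offs and the answer rule for items 18 and 24 should be reconciled in the text. This point takes no position on the referral or reporting rules themselves.

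The cost is a sentence or two in Table 1, one reference and a brief check of the code. There is no statistical downside.

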
Initial evidence from prior studies is promising, however, the study designs lack rigor and comprehensiveness. In these studies, early administration of mother's own milk or donor's milk shortly after birth supported oral mechanical stimulation and subsequent maturation of suckling and swallowing skills.^{28,29} It is evidenced by less episodes of feeding intolerance and shorter duration to full oral feeding.^{28,29} Researchers also found that the intervention offered immunoprotection as evidenced by lower pathogenic microbacterial colonization of the gastrointestinal tract and incidence of ventilator-associated pneumonia.²⁹ The intervention reduced duration of oxygen support, length of stay, and cost of care.²⁷⁻³⁰ However, the potential efficacy of M-MILK to attenuate the effects of early life toxic stress on epigenetic modifications and gut microbiome is unknown. This gap leads to a missed opportunity for individualized neonatal care and early parental involvement in the NICU which could protect very and extremely preterm infants against early life toxic stress. There is an urgent need to address this knowledge gap and determine the efficacy of M-MILK.

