The M-MILK pilot study ($N = 12$) is a 2-group, 6 per group, parallel design, and longitudinal randomized controlled trial. We will recruit preterm infants who are born between 22 to 33 weeks gestational age. We will compare the outcomes between the M-MILK and attention control groups. Infants will be enrolled into the study as soon as possible after they are admitted to the NICU. If infants are in the M-MILK group, M-MILK will begin on day 3 of life after every hands-on care and during the beginning of a full gavage feeding. We will measure outcomes using validated methodologies at baseline (enrollment), 34 weeks PMA, discharge, and 2 months CA.

b. Setting

The M-MILK pilot study will be conducted in a level III NICU at LUMC (Maywood, IL). The hospital provides care to families with diverse racial, ethnic, and socioeconomic backgrounds. The nursing staff are predominantly registered nurses and advanced nurse practitioners, and the physicians are board certified

neonatologists. Infants are fed using mother's own milk, donor milk, and/or formula. However, we will only include infants who receive mother's own milk or donor's milk.

c. Sample

We will enroll 12 preterm infants (6 per group). Anticipated a 40% attrition rate, we expect the final sample size to be 12 preterm infants. Estimates of average values and variability of continuous measures are acceptable at this sample size using the "rule of 12" as recommended.³¹

VII. Study Procedures

a. Subject Selection Procedures

i. Inclusion/Exclusion Criteria

Inclusion criteria

- Born between 22 to 33 weeks gestational age
- Mother is pumping and infant is receiving mother's own milk and/or donor's milk to be in the intervention group.

Exclusion criteria

- Congenital abnormalities in the digestive, e.g., clef lip and palate, omphalocele
- Necrotizing enterocolitis
- Congenital heart disease that requires surgery

ii. Screening procedures

After infants are admitted to the NICU, we will review their electronic medical records to screen for eligible infants according to the inclusion and exclusion criteria. Once an infant is enrolled into the study, the screening period continues until NICU discharge. The infant will be classified as screen failed and excluded if he/she develops any of the exclusion criteria.

iii. Recruitment Procedures

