The M-MILK group will have access to the educational materials regarding preterm infant care such as Your Guide to Neonatal Intensive Care Unit, Breastfeeding in the NICU, and M-MILK Toolkit video. We will provide parents with two scent hearts to wear and bring back to place near the infant's face. Parents will perform routine care such as taking temperature, bathing, changing diapers, reading, feeding, holding hands, as well as M-MILK when appropriate. Parents will receive an automatic daily text in the morning with a link to report their daily activities with infants when they visit the NICU.

The M-MILK Intervention Protocol is a modified and improved version of previous protocols. This M-MILK protocol is carefully designed by a team of neonatal experts, with a strong focus on developmentally appropriate, trauma informed care, and family friendly language. M-MILK is implemented at day 3 of life even if the infant requires respiratory support and/or mechanical ventilation. M-MILK is implemented after every hands-on care and during the beginning of a full gavage feeding. Infants receive M-MILK as droplets via a 1-ml syringe. In our NICU, oral feeding attempts are initiated at approximately 33 to 34 weeks PMA and based on the infant's pre-feeding cues. M-MILK is not offered with oral feeding attempts since the feeding itself is considered a positive experience. We will use either mother's own milk and or donor's milk depending on availability. Infants may receive up to 1 mL of milk each time based on their cues and responses. The 1 mL volume intake is included as part of their oral caloric intake. M-MILK is provided by the infant's nurse or parents. Parents are encouraged and supported to provide M-MILK when appropriate with the nurse's supervision.

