Neurodevelopment	
Neurodevelopment will be evaluated via the Neurobehavioral Assessment of the Preterm Infants (NAPI) at discharge.⁴²⁻⁴⁵ The PI will train a Research Nurse to criterion of $\geq 90\%$ agreement. A Research Nurse (who is blinded to the infant's group assignment) will conduct, rate and video record the NAPI assessment. A secondary trained evaluator will code 20% of the videos to assure continued reliability. The Neurobehavioral Assessment of the Preterm Infants (NAPI, 73 items, 32-37 weeks PMA): summary scores, normed referenced means, standard deviation, 7 clusters: scarf sign, motor development & vigor, popliteal angle, alertness and orientation, irritability, quality of cry, & percent sleep ratings.⁴²⁻⁴⁵ Construct validity, face validity, & sensitivity of the NAPI were described using an index of medical complications & general movements.^{43,44,46} Inter-rater reliability coefficient was 0.67 to 0.97.⁴⁷
 
Neurodevelopment will also be evaluated via the Ages and Stage Questionnaire (ASQ-3), completed by parents at 2 months CA.⁴⁸ The ASQ-3 is a developmental screening tool that pinpoints developmental progress in children between the ages of one month to years. It is a validated and standardized screening tool based on parental report that reliably assesses five key developmental domains: communication, fine and gross motor, problem solving, and personal-social skills. The ASQ-3 has strong concurrent validity ($r = 0.85$), 2-week test-retest reliability ($r = 0.75-0.82$), interobserver reliability ($r = 0.43-0.69$), and internal consistency ($\alpha = 0.51-0.87$).⁴⁸ The ASQ-3 provides cutoff scores to indicate possible delay as follows: communication, gross motor, fine motor, problem solving, and personal-social. The AAP reports the ASQ-3 sensitivity range to be 0.70 to 0.90 and specificity to be 0.76 to 0.91.⁴⁹ The five scored domains include communication, gross motor, fine motor, problem-solving, and personal-social. Scores of 10, 5, and 0 are applied, respectively, to caregiver responses of "yes," "sometimes," and "not yet" to 30 items. The scores are tabulated for each domain and are further categorized into a color-coded chart based on score interpretation. "Above cutoff" is considered typical development and is defined as any score in the white area (higher than 1 SD below the mean); scores within the gray area indicate the "monitoring zone" in which the child should be observed and another screening may be desirable in a few months (1-2 SD below the mean); and scores within the black area are "below cutoff" and indicate the child may be at risk for developmental delays and should be referred for further assessment (2 SD below mean).⁵⁰
	T3 NAPI T4 ASQ-3

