Charges and costs of care	Healthcare use and associated charges and costs of the NICU hospitalization and 2 months CA care will be extracted from LUMC's electronic health and billing records. For infants receiving care outside LUMC 2 months CA, we will ask the parents about the extent and types of healthcare received outside LUMC. We will evaluate healthcare use, costs, and charges between the M-MILK and control groups. We will also describe the extent and types of healthcare use 2 months CA for infants receiving care outside LUMC at discharge. In the R01 trial, we will use activity-based costing approach to calculate the time and resources costs of delivering the M-MILK intervention by nurses and parents (which may not be fully reflected in the health system billing records), and query NICU hospitalization and 2 months CA healthcare use, charges, and costs to calculate total benefits and costs of M-MILK Intervention vs. control group.	T3 & T4
M-MILK Acceptability Questionnaire	The M-MILK Acceptability Questionnaire will be completed by parents at discharge. The nurses will complete the M-MILK Acceptability Questionnaire at the end of the entire study.	T3 M-MILK Acceptability Questionnaire

Note. EPIC = electronic medical record; GA = gestational age; PMA = postmenstrual age; CA = corrected age; Ongoing = throughout hospitalization from enrollment to discharge; T0 = baseline; T1 = 34 weeks PMA; T2 = oral feeding initiation; T3 = discharge; T4 = 2 months CA

ii. Procedures

Figure 2. After informed consent is obtained, infants will be randomized into: Group 1 (M-MILK) and Group 2 (attention control). All data collection will be conducted in the same manner and at the planned time points for both groups. For all infants, we will collect infant characteristics, NISS, and family NICU activities daily ongoing from EPIC and self-report. All parents will receive an automatic daily text in the morning with a link to report their daily activities with infants when they come to the NICU. All parents are signing up for daily texts for up to 20 weeks to complete daily activities report every day during their participation. All parents will also receive a weekly phone call from a research nurse from enrollment until discharge. M-MILK is primarily implemented by nurses or parents. **At baseline (T0)**, we will conduct the EPDS assessment, and collect parent characteristics,

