buccal swab and fecal samples. For infants in the M-MILK group, the clinical team will place an order in EPIC for M-MILK to be provided starting on day 3 of life according to the M-MILK protocol. We will also schedule an in-person 30-minute M-MILK training session with parents in the M-MILK group, within 1 week of enrollment, provided by a research nurse. Parents in the M-MILK group are encouraged and supported to provide M-MILK when appropriate with the nurse's supervision. **At 34 weeks PMA (T1)**, we will collect PBQ, buccal swab and fecal samples. **At oral feeding initiation (T2)**, we will collect the EFS, and NCAST-Feeding video recording. Day of initiation of oral feeding is defined as the first of at least two consecutive days when the infant is able to orally consume $\geq 10\%$ of their prescribed feedings. Infants will be fed by nurses, speech therapist, or PI. We will implement the same feeding protocol, e.g., side-lying and swaddling during feeding. **During the week of planned discharge (T3)**, we will conduct EPDS, PSS: NICU, PDR, PBQ, Pumping and Breastfeeding, NMI, NAPI, and EFS assessments. We will collect NCAST-Feeding video recording, buccal swab and fecal samples. For the NCAST-Feeding video recording, both parents and infants will be recorded. Parents will also complete the M-MILK Acceptability Questionnaire at T3. For EFS and NAPI assessments, we will video record the assessments, when possible, to obtain videos for inter-rater reliability. **At 2 months CA (T4)**, we will send parents the fecal and buccal sample collection kits via USPS mail service. We will also conduct a phone/Zoom interview to complete the EPDS, PBQ, ASQ-3, and NeoEAT assessments. During the phone/Zoom interview, we will also provide parents instructions on how to collect buccal and fecal samples and securely send them back to us.

VIII. Safety Monitoring Plan

a. Potential Risk

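### The NAPI is described for 32-37 weeks PMA but scheduled at discharge with no age window, so some infants may be tested outside its range and at ages that could differ by arm

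*Combined protocol and SAP*

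**What the plan says.** The Neurodevelopment row of Table 1 (Section VII.a.vi.1, Measures) describes "The Neurobehavioral Assessment of the Preterm Infants (NAPI, 73 items, 32-37 weeks PMA" and says that scores come with reference means and an SD. The same row sets the time: "Neurodevelopment will be evaluated via the Neurobehavioral Assessment of the Preterm Infants (NAPI) at discharge". The Procedures text agrees. It lists, for the week of planned discharge (T3), "PSS: NICU, PDR, PBQ, Pumping and Breastfeeding, NMI, NAPI, and EFS assessments". Neither place gives a PMA window for T3, a rule for an infant already past 37 weeks, or a way to score one.

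Other parts of the protocol bear on this:

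- **Eligibility** (Section VI.a, Design; Section VII.a.i): infants "born between 22 to 33 weeks gestational age".
- **The 34-week visit (T1)** has a fixed age inside the NAPI range, but the NAPI is not done there: "we will collect PBQ, buccal swab and fecal samples".
- **Feeding** (Section VII.a.v.1): "In our NICU, oral feeding attempts are initiated at approximately 33 to 34 weeks PMA".
- **EFS** (Table 1): also given at discharge, and described for 32-50 weeks PMA.
- **Earlier studies** (Section III, Background): "The intervention reduced duration of oxygen support, length of stay, and cost of care".
- **Daily texts** (Procedures): "All parents are signing up for daily texts for up to 20 weeks".
- **PMA at discharge** is collected (Table 1, Infant characteristics). Section IX plans descriptive statistics and intent-to-treat comparisons, and states no use of PMA in handling NAPI scores.

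**The concern.** Discharge is an event, not an age. Tying a test with a stated age range to that event leaves the age at testing uncontrolled, with three consequences.

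1. An infant who goes home after the upper limit is scored on an instrument whose stated range, and presumably its reference values, do not cover that age.
2. Age at discharge is determined after randomization. If the intervention changes length of stay, the arms are tested at different ages, and a difference in NAPI scores cannot be cleanly attributed to treatment.
3. Aim 3 is to obtain variability data for sizing the R01. A NAPI SD from this schedule combines variation between infants with variation in test age.

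The gap is specific to the NAPI: the EFS at the same visit has a stated range that runs to 50 weeks.

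**Working it through.** The plan gives no figure to reproduce here. The check uses its stated ages plus labelled assumptions.

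**Step 1. Can infants leave the range?** PMA at test = gestational age at birth + weeks from birth to discharge. To be tested by 37w0d, the longest possible stay is 37 minus gestational age at birth:

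| Born at (weeks) | Longest stay for testing by 37w0d |
|---|---|
| 22 | 37 - 22 = 15 weeks |
| 24 | 13 weeks |
| 26 | 11 weeks |
| 28 | 9 weeks |
| 33 | 4 weeks |

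Add one week if the range is read as running through 37w6d. With oral feeding attempts starting at about 33 to 34 weeks, an infant has about 37 - 34 = 3 to 37 - 33 = 4 weeks from first attempts to discharge while still in range. As an extreme, birth at 22 weeks followed by a stay as long as the 20-week limit on texts would end at 22 + 20 = 42 weeks PMA. So testing past the range is possible under the plan as written.

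**Step 2. What share?** The documents do not give discharge PMA. Assume it is normal with mean m and SD s. The share beyond a limit L is 1 - Φ((L - m)/s). With s = 2 weeks:

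| Assumed mean m | After 37w0d (L = 37) | At 38w0d or later (L = 38) |
|---|---|---|
| 36 | 31% | 16% |
| 37 | 50% | 31% |
| 38 | 69% | 50% |
| 39 | 84% | 69% |

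For example, m = 36 and L = 38 gives 1 - Φ(1.0) = 0.16. The assumed SD also matters. Over s = 1 to 3 weeks with L = 38, the share is 2% to 25% at m = 36 and 63% to 84% at m = 39. For the 12 infants in Section VI, 16% to 69% is 0.16 × 12 = 1.9 to 0.69 × 12 = 8.3, or about 2 to 8.

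**Step 3. Effect on the contrast.** Suppose a NAPI score changes by b same-age SDs per week of PMA, and one arm goes home d weeks earlier. The contrast then shifts by b × d from age alone. With d = 1 and b assumed between 0.1 and 0.5, the shift is 0.1 to 0.5 SD. The documents give neither b nor d.

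**Step 4. Effect on the SD.** If test age has SD s and is linearly related to the score, the SD is multiplied by √(1 + (b × s)²) relative to testing at one age. The sample size for a fixed difference is multiplied by 1 + (b × s)². With s = 2:

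| Assumed b | SD multiplied by | Sample size multiplied by |
|---|---|---|
| 0.1 | 1.02 | 1.04 |
| 0.25 | 1.12 | 1.25 |
| 0.5 | 1.41 | 2.0 |

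This comparison matters only if the R01 tests at a fixed age.

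**The case against.** Several stronger readings are tempting, and the documents do not support them.

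- **That many of the most immature infants would be tested out of range.** No discharge ages are given, so this cannot be counted. Eligibility runs up to 33 weeks, and infants who develop an exclusion condition such as necrotizing enterocolitis are removed, which may take out some long stays.
- **That the protocol plans stays of up to 20 weeks.** That figure limits the sign-up for daily texts. Adding it to the lowest gestational age gives an extreme, not an expected case.
- **That the protocol expects M-MILK to shorten stay.** The Background reports this from earlier studies, whose designs it calls insufficiently rigorous. It is not stated as a hypothesis of this pilot.
- **That the comparison is biased against M-MILK.** This needs shorter stay to recur and the relevant scores to rise with age. The seven clusters include irritability, quality of cry and percent sleep, and Table 1 does not say how each changes with age. Age-specific norms, if used, would remove part of the effect inside the range.
- **That the R01 SD will be inflated.** If the R01 also tests at discharge, the discharge SD is the right one. Its test time is not stated, nor is the NAPI named as its sizing outcome.

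It is also fair that PMA at discharge is recorded, so age at testing is known to within about a week. No feasibility criterion depends on the NAPI, and the analysis is largely descriptive.

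These limits make the consequences conditional and lower their weight. They do not remove the mismatch: the plan states an age range and then schedules the test with nothing to keep it inside that range.

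**Conclusion.** The point holds in a limited form. The stated NAPI range and its timing at discharge are not reconciled, and following the plan can produce scores outside 32-37 weeks PMA, at an age fixed only after randomization. The 16% to 69% is an illustration that rests wholly on an assumed mean discharge PMA of 36 to 39 weeks, an SD of 2 weeks and a cut at 38w0d. It is not an estimate for this unit. Mixing of treatment with age depends on length of stay differing by arm, and the excess in the SD depends on the R01 testing at a fixed age. This is a cheap improvement that the sponsor should make. It does not threaten the pilot's feasibility aims.

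**What to change.** Give the NAPI to both arms in a fixed PMA window inside its stated range, for example the week of 36 weeks PMA, or at discharge if that comes first. Record PMA at testing, report it by arm, and state how a missed window is handled. The clause for earlier discharge leaves some difference in test age, but only among infants who go home before the window.

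If discharge timing is kept:

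- report PMA at assessment by arm;
- flag scores obtained past 37 weeks as outside the stated range, and say whether 37w6d counts as inside;
- treat any PMA-adjusted comparison as a sensitivity analysis only. Discharge age may itself be affected by treatment, and adjustment cannot supply norms for later ages.

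The preferred change keeps the same single test and the same blinded Research Nurse. The protocol already has a fixed-PMA visit at 34 weeks, so scheduling by PMA is not new to the team. The cost is some extra scheduling, a NAPI date that may differ from the other T3 measures, and a score that describes the infant at a set age rather than at discharge.
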